8.5.2 Analysis

All laboratory data parameters and visits will include flags for values above or below laboratory reference ranges. Toxicity grades will be assigned programmatically by applying the CTCAE v5guidelines. Only results with assessment dates through the end of the safety observation period (see Section 4.5) will be tabulated in summary tables.

Laboratory summaries will be presented in SI units. Continuous laboratory test results will be summarized by treatment group using descriptive statistics for actual values and for changes from baseline by scheduled visit. Means and respective standard errors may also be presented at each scheduled visit (with visits shown on x-axis) for some laboratory parameters. For continuous laboratory test results which are below or above the quantification level, the imputed values as described in Appendix C will be used for deriving the grade and then summarized.

Tables summarizing the incidence of laboratory abnormalities by maximum post-baseline CTCAE grade overall and by baseline grade will be presented. Frequencies of laboratory abnormalities of worsening $\geq +1$ and +2 change from baseline to worst grade value after first dose will also be summarized.

In addition, the following summaries will also be presented:

- A. Liver function abnormalities will be assessed as follows:
 - Shift from baseline based on normal ranges
 - Subject-incidence of treatment-emergent liver function test abnormalities according to baseline criteria
 - >3xULN (ALT or AST), <2xULN ALP, and >2xULN Total Bilirubin
 - >3xULN (ALT or AST), >=2xULN ALP, and >2xULN Total Bilirubin

- B. For renal failure surveillance, a summary of subjects meeting renal failure laboratory screening criteria as shown below will be provided:
 - Serum creatinine >= 3.0xULN and >= 2.0x baseline value or
 - Estimated glomerular filtration rate (eGFR) \leq 50% of the baseline value or
 - eGFR < 30 mL/min/1.73 m² and ≥ 25% reduction from the baseline value eGFR = 186 x (Creatinine in mmol per L / 88.4)-1.154 x (Age)-0.203 x (0.742 if female) x (1.210 if black) [MDRD186 formula on the National Kidney Foundation FAQ, #10: https://www.kidney.org/sites/default/files/docs/12-10-4004 abe faqs aboutgfrrev1b singleb.pdf]
- C. Categorical summaries for baseline status for TSH and Free T4 will be presented. In addition categorical summaries for post-baseline TSH and Free T4 status among subjects with TSH and Free T4 in the normal range at baseline will also be presented.

For descriptive summaries for change from baseline analyses, only central lab results will be considered. For analyses of shift in grade from baseline or worst grade after baseline, all available results will be considered regardless of whether from the central or local lab.

Table 7: Laboratory Summaries

	Include Central Lab	Include Local Lab
Summary Type	results?	results?
Subject Incidence of Treatment Emergent Laboratory		
Abnormalities in Selected Laboratory Tests by CTCAE Grade	Y	Y
Change from Baseline in Laboratory Values	Y	N
Shift from Baseline in Laboratory Values by CTCAE Grade	Y	Y
Shift from Baseline of at Least 2 Grades by CTCAE Grade	Y	Y
Shift from Baseline in Laboratory Values by High/Low/Normal	Y	Y
Shift from Baseline in Laboratory Values by Sponsor-defined		
Grades	Y	Y
Subject Incidence of Laboratory Abnormalities with a Between-		
Arm Difference of ≥5% (All Grades) or ≥2% (Grades 3-4)	Y	Y
Subject Incidence of Treatment-Emergent Liver Function Test		
Abnormalities According to Baseline Criteria	Y	Y
Subject Incidence of Treatment-Emergent Renal Function Test		
Abnormalities According to Baseline Criteria	Y	Y

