- 7. The subject is  $\geq 18$  years old on the day of consent.
- 8. The subject has an ECOG (Eastern Cooperative Oncology Group) status  $\leq 1$  at screening.
- 9. The subject has adequate organ and marrow function, based upon the following laboratory criteria from assessments performed within 28 days before randomization
  - a. Absolute neutrophil count (ANC)  $\geq 1500/\text{mm}^3$
  - b. Platelets  $\geq 100,000/\text{mm}^3$
  - c. Hemoglobin  $\geq 9 \text{ g/dL}$
  - d. Total bilirubin  $\leq 1.5$  x the upper limit of normal (ULN). For subjects with known Gilbert's disease, total bilirubin  $\leq 3.0$  mg/dL.
  - e. Alanine aminotransferase (ALT) and aspartate aminotransferase (AST) < 3.0 x ULN
  - f. Serum creatinine ≤ 1.5 x ULN or creatinine clearance ≥ 50 mL/min (using the Cockcroft-Gault equation: CrCl (mL/min) = (140 age) x wt (kg) / (serum creatinine [mg/dL] x 72); for females multiply by 0.85
  - g. Urine protein/creatinine ratio (UPCR) ≤ 1 mg/mg (≤ 113.1 mg/mmol) or 24-hour urine protein < 1 g
  - h. Prothrombin time (PT)/INR or partial thromboplastin time (PTT) test results at screening  $\leq 1.3$  x the laboratory ULN
- 10. The subject is capable of understanding and complying with the protocol requirements and has signed the informed consent document.
- 11. Sexually active fertile subjects and their partners must agree to use medically accepted methods of contraception (defined in Appendix E) during the course of the study and for 4 months after the last dose of study treatment.
- 12. Female subjects of childbearing potential must not be pregnant at screening. Females of childbearing potential are defined as premenopausal females capable of becoming pregnant (ie, females who have had any evidence of menses in the past 12 months, with the exception of those who had prior hysterectomy). However, women who have been amenorrheic for 12 or more months are still considered to be of childbearing potential if the amenorrhea is possibly due to prior chemotherapy, antiestrogens, ovarian suppression or other reasons.

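### The SAP's eGFR formula pairs creatinine in mmol/L with the micromol/L divisor 88.4, so if programmed as written one of its three renal-failure screening criteria can flag nobody

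*SAP*

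**What the plan says.** SAP 8.5.2, item B, plans a summary of subjects who meet any one of three laboratory criteria for renal failure:

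- Criterion 1, creatinine only: "Serum creatinine >= 3.0xULN and >= 2.0x baseline value or"
- Criterion 2, relative eGFR: at or below "50% of the baseline value or"
- Criterion 3, absolute eGFR plus a relative fall: "eGFR < 30 mL/min/1.73 m² and ≥ 25% reduction from the baseline value"

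The eGFR for criteria 2 and 3 is defined as "eGFR = 186 x (Creatinine in mmol per L / 88.4)-1.154 x (Age)-0.203 x (0.742 if female", followed by a race multiplier and a named source: "1.210 if black) [MDRD186 formula on the National Kidney Foundation FAQ, #10". The same section says "Laboratory summaries will be presented in SI units". That does not settle the unit, because mmol/L and micromol/L are both SI-based. No other part of the SAP gives a different eGFR formula.

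SAP Table 7 includes a row for this output, beginning "Subject Incidence of Treatment-Emergent Renal Function Test". The SAP version history lists the renal screening criteria and the updated eGFR calculation among the V2.0 changes.

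**The concern.** Dividing by 88.4 is meant to turn a molar creatinine into mg/dL, the scale on which the constants 186 and -1.154 work. If 88.4 does not match the stated unit, creatinine enters the formula 1,000 times too small. The negative power then makes eGFR far too large to compare with a threshold of 30.

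At stake is a pre-specified screen that would return zero in both arms by construction. In a trial comparing the tolerability of two doses, a reader could take that zero as reassurance.

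**Working it through.** **Inputs**

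- Formula, exponents and criteria: SAP 8.5.2, item B. The exponents have lost their superscripts in the text and are read as -1.154 and -0.203.
- Creatinine mass-to-mole factor: Protocol inclusion criterion 9g, "1 mg/mg (≤ 113.1 mg/mmol". This means 1 mmol of creatinine is 113.1 mg.
- Renal entry rule: Protocol inclusion criterion 9f, creatinine no more than 1.5 x ULN, or Cockcroft-Gault clearance of at least 50 mL/min.

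**1. Which unit does 88.4 belong to?**

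1 mg/dL = 10 mg/L, and 10/113.1 = 0.0884 mmol/L = 88.4 micromol/L. The SAP's 88.4 is reproduced for micromol/L. For mmol/L the divisor would be 0.0884. SAP 8.5.1 pairs 1.0 mg/mg with 121.0 mg/mmol in its UPCR grades. That factor gives 10/121.0 = 0.083 mmol/L, still three orders of magnitude from 88.4.

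**2. Size of the inflation**

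Literal eGFR / unit-consistent eGFR = (1/1000)^-1.154 = 1000^1.154 = 10^3.462 = 2,897. It is the same for every age, sex, race and creatinine value.

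**3. Values (non-black men)**

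| Age | Creatinine (micromol/L) | Unit-consistent eGFR | Literal eGFR |
|---|---|---|---|
| 55 | 88.4 | 82.5 | 238,902 |
| 60 | 300 | 186 x (300/88.4)^-1.154 x 60^-0.203 = 19.8 | about 57,300 |
| 55 | 1,000 | 5.0 | 14,535 |

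Across the profiles tried (ages 18 to 86, both sexes, creatinine up to 1,000 micromol/L), the lowest literal value was 9,850.

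**4. Can the literal formula fall below 30?**

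For a 60-year-old non-black man, eGFR is 30 at creatinine 88.4 x (186 x 60^-0.203 / 30)^(1/1.154) = 209. With consistent units that is 209 micromol/L. Taken literally it is 209 mmol/L, which is not physiologically possible.

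**5. Which criteria are affected?**

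- Criterion 2 depends only on eGFR(post)/eGFR(baseline) = (baseline creatinine / post creatinine)^1.154, taking age as fixed. The unit cancels. A halving of eGFR corresponds to a creatinine rise of 2^(1/1.154) = 1.82-fold.
- Criterion 1 contains no eGFR. It needs creatinine at least 2.0 times baseline, which exceeds 1.82, so anyone meeting it also meets criterion 2 at that visit.
- Criterion 3 has a relative part that still works: a 25% fall is a creatinine rise of (1/0.75)^(1/1.154) = 1.28-fold. Its absolute part, below 30, cannot be met, so the criterion is disabled.

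**6. Who is lost?**

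Those whom only criterion 3 would catch: true eGFR falls below 30, with a loss of at least 25% but less than 50%. The creatinine rise is therefore about 1.28- to 1.82-fold, and baseline eGFR is below 30/0.5 = 60. Nobody in this band meets criterion 1 at that visit, because that needs a doubling.

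Example: a 65-year-old non-black woman goes from 130 to 190 micromol/L, a rise of 190/130 = 1.46. Her true eGFR falls from 37.9 to 24.5, about 35%. She meets criterion 3 only, and the literal formula returns about 70,900. The documents give no ULN. She would be eligible under 9f if the laboratory ULN is at least 130/1.5 = 86.7 micromol/L. She would also be eligible by clearance at about 83 kg or more: (75 x 83 x 0.85)/(72 x 1.47) = 50 mL/min.

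**The case against.** The strongest objection is that this is one letter. A micro sign can become an m when a PDF is converted to text, and this same line has lost its superscripts. If the source file says micromol, the point falls. The doubt is fair but not shown: the SAP text keeps other special characters such as the Greek alpha, writes micro as u in its CEA unit (section 5.5), and here spells out the unit in words.

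Second, the SAP names the formula it intends, so a programmer may well use micromol/L. An eGFR near 239,000 would be hard to miss, and SAP section 11 provides data validation and a data review meeting. This stands as a reason to expect the error to be caught. It does not make the written specification correct.

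Third, the reach is limited, and this stands in full. A reader might infer that the whole renal-failure summary fails, or that renal toxicity would go unseen. The documents do not support that:

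- Two of the three criteria work as intended.
- Anyone who starts at 60 or above and falls below 30 has lost at least half and is caught by criterion 2.
- Table 6 also summarises raised creatinine and reduced creatinine clearance by CTCAE grade, and renal adverse events enter the general AE tables. None of these depends on this formula.

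A reader might also infer that impossible eGFR values will be published. The section specifies a summary of subjects meeting criteria and names no eGFR listing.

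**Conclusion.** The formula is wrong as written. Followed literally, it inflates every eGFR about 2,897-fold, and criterion 3 can flag nobody in either arm. Criteria 1 and 2 are intact. The loss is confined to subjects with baseline eGFR below 60 who fall below 30 on a creatinine rise of about 1.28- to 1.82-fold. Criterion 9f makes such subjects eligible. The documents do not show that any were enrolled, and the number may be small.

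It would go too far to say that the renal comparison of the two doses is biased by a known amount. The protocol plans no formal safety comparison (section 9.4), the SAP treats any such comparison as exploratory (section 8), and PFS and ORR are untouched.

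The conclusion assumes that the source SAP reads as the public text does and that the derivation follows it literally. The unit argument itself rests only on the protocol's 113.1 mg/mmol and on the SAP's own threshold of 30. The cited kidney-foundation document was not consulted.

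**What to change.** In SAP 8.5.2, item B, state creatinine in micromol/L divided by 88.4, or equivalently mmol/L divided by 0.0884. First confirm the unit in the source SAP file. Then check that the derivation program uses the same unit; a 60-year-old non-black man at 300 micromol/L should return 19.8. Section 4.8 already provides for minor corrections by addendum before unblinding.

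The cost is one unit in the text and one check of the program, with a re-run of the renal summary if it was derived literally. No new data are needed, and no threshold or criterion changes.

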8.6 Vital Signs

8.6.1 Variables

The following vital signs will be summarized for subjects in the safety population

Weight

- Systolic blood pressure (mmHg)
- Diastolic blood pressure (mmHg)

8.6.2 Analysis

Summary tables of vital signs and change from baseline for each study visit will be presented. Only results with assessment dates through the end of the safety observation period (see Section 4.5) will be considered for the summaries.

Subject-incidence of clinically meaningful vital sign results as shown below will also be presented:

- Subjects who got worse since baseline and met the following blood pressure criteria on 2 or more visits (need not be consecutive) after first dose (JNC criteria were modified and also include single measurement per time point when triplicate assessments were unavailable; JAMA 2003:289:2560):
 - o Pre-hypertension: SBP 120-139 mmHg or DBP 80-89 mmHg
 - Stage 1: SBP 140-159 mmHg or DBP 90-99 mmHg
 - \circ Stage 2: (SBP >= 160 mmHg and DBP <120) or DBP 100-119 mmHg
 - \circ Stage 3: DBP \geq 120 mmHg
- Proportion of subjects with weight loss $\geq 10\%$ after first dose

8.7 ECOG Performance Status

For the purpose of evaluating safety, ECOG will be summarized as shift from baseline tables for, at minimum, the worst value recorded after the initiation of study treatment. Only results with assessment dates through the end of the safety observation period (see Section 4.6) will be tabulated in summary tables.

Frequencies of ECOG worsening of $\geq +1$ and +2 change from baseline to worst value after first dose will also be summarized.

8.8 Electrocardiogram

Only results with assessment dates through the end of the safety observation period (see Section 4.5) will be considered for summaries. The following categorical summaries will be presented per investigator and per ERT review:

- Number of subjects with triplicate average QTc > 500 ms after first dose
- Number of subjects with increase in triplicate average QTc from baseline of >60ms

For the above summaries, the QTcF average was calculated based on all consecutive test results obtained at that time point.

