## 1.4.3.1 Overall Safety Profile

Consult the Investigator's Brochure for the most updated safety data on cabozantinib.

As of 28 February 2014, AE data are available for more than 1300 subjects who have been dosed with single-agent cabozantinib in clinical studies. These subjects have been treated with cabozantinib at malate salt weight doses ranging from 0.08 to 11.52 mg/kg (0.064 to 9.22 mg/kg FBE weight) on an intermittent dosing schedule and from 25 mg (20 mg FBE weight) to 265 mg (212 mg FBE weight) on a fixed daily dosing schedule. Available pooled data in the clinical database for the 1368 subjects who received single-agent cabozantinib show that the most frequently (> 20%) observed AEs regardless of causality were fatigue, diarrhea, nausea,

decreased appetite, weight decreased, palmar-plantar erythrodysesthesia syndrome (PPES), vomiting, constipation, hypertension, dysgeusia, dysphonia, aspartate aminotransferase (AST) increased, abdominal pain, dyspnea, headache, rash, and alanine aminotransferase (ALT) increased. Effects that may be related to inhibition of VEGF, including hypertension, thromboembolic events, GI perforation, fistula formation, hemorrhage, wound dehiscence, proteinuria, osteonecrosis of the jaw (ONJ), and reversible posterior leukoencephalopathy syndrome (RPLS), have been observed in clinical studies with cabozantinib, either as a single-agent or as part of a combination treatment.

Electrocardiogram (ECG) data from the double blind, placebo controlled XL184-301 Study in subjects with progressive, metastatic MTC (at a dose of 140 mg FBE weight) showed a mean increase in the QT interval corrected for heart rate using the Fridericia formula (QTcF) of 10 - 15 ms at 4 weeks after initiating treatment. No subjects had a QTcF > 500 msec.

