# 6.5.2.10 Corrected QTc Prolongation

The effect of orally administered cabozantinib at 140 mg/day (FBE) on QTc interval was evaluated in a randomized, double-blinded, placebo-controlled Phase 3 study in subjects with MTC. A mean increase in QT interval corrected by Fridericia (QTcF) of 10-15 ms was observed at 4 weeks after initiating cabozantinib. A concentration-QTc relationship could not be

<sup>a Study treatment includes both cabozantinib and matched placebo.

definitively established. Changes in cardiac wave form morphology or new rhythms were not observed. Thus far no cabozantinib-treated subjects have had a treatment-emergent QTcF > 500 ms. Accordingly, subjects in this study will be monitored for potential QT effects.

Only subjects with a baseline QTcF interval corrected by Fridericia (QTcF)  $\leq$  500 ms are eligible for this study. Subjects will have ECGs performed at times designated by the protocol (Section 5.5.4 and Appendix A).

If at any time on study there is an increase in QTcF interval to an absolute value > 500 ms or an increase of >60 ms above baseline, two additional ECGs must be performed with intervals not less than 3 min apart within 30 min after the initial ECG.

If the average QTcF from the three ECGs is > 500 ms or an increase >60 ms above baseline, the following actions must be taken:

- Withhold study treatment
- Immediately notify the Sponsor
- Hospitalize symptomatic subjects (eg, with palpitations, dizziness, syncope, orthostatic hypotension, a significant ventricular arrhythmia on ECG) for a thorough cardiology evaluation and treatment according to standard clinical practice
- Consider cardiology consultation for asymptomatic subjects for evaluation and management
- Check electrolytes, especially magnesium, potassium, and calcium; correct abnormalities as clinically indicated
- Check concomitant medications for any medication that may have contributed to QTc prolongation, and if possible, discontinue these medications (see http://www.qtdrugs.org)
- Send ECGs to central ECG laboratory (see ECG study manual)
- Repeat ECG triplicates hourly until the average QTcF is  $\leq$  500 ms or an increase of  $\leq$  60 ms above baseline, or otherwise determined by consultation with a cardiologist

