# 9.4.3 Other Safety Endpoints

Changes or shifts from baseline in vital signs, ECOG and QTc interval will be summarized by treatment arm.

The number of subjects experiencing dose reduction, delay, and/or discontinuation due to an AE will be provided.

Concomitant medications will be standardized using the World Health Organization (WHO) drug dictionary and summarized by class and preferred term.

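### SAP 8.8 narrows the QTc analysis to two threshold counts, so the known mean QTcF increase of 10-15 ms would not be estimated in either dose arm

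*SAP*

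**What the plan says.** Protocol 9.4.3 (Other Safety Endpoints) makes one commitment covering three items: "Changes or shifts from baseline in vital signs, ECOG and QTc interval will be summarized by treatment arm".

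The SAP treats the three items differently.

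- **Vital signs (SAP 8.6.2):** "Summary tables of vital signs and change from baseline for each study visit will be presented".
- **ECOG (SAP 8.7):** "ECOG will be summarized as shift from baseline tables for, at minimum, the worst value recorded".
- **QTc (SAP 8.8):** "The following categorical summaries will be presented per investigator and per ERT review". Two follow: "Number of subjects with triplicate average QTc > 500 ms after first dose" and "Number of subjects with increase in triplicate average QTc from baseline of >60ms".

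The protocol also describes the QTc signal already seen. For 140 mg in XL184-301, Section 6.5.2.10 states: "A mean increase in QT interval corrected by Fridericia (QTcF) of 10-15 ms was observed", at 4 weeks. Section 1.4.3.1 adds: "No subjects had a QTcF > 500 msec". Protocol Appendix A schedules ECGs before the first dose, at W5D1, W9D1 and W13D1, and every 12 weeks after that.

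**The concern.** The known effect is a shift in the mean. The planned summaries count individual outliers at cut-offs four or more times the size of that shift (60 ms against 10-15 ms), or at an absolute level that no subject reached in XL184-301. A table of two such counts does not say how far QTcF moved on either dose.

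This matters because better tolerability is the stated reason for testing 60 mg (Protocol 1.5.1 and 1.5.5). Protocol 6.5.2.10 also says that a relation between concentration and QTc could not be firmly established. A randomised comparison of two doses with serial ECGs is a good setting in which to describe this, and the plan as written does not use the data that way. No efficacy endpoint, significance level or QTc management rule is affected.

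**Working it through.** **Is the gap filled elsewhere in the SAP?** No.

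- The opening of Section 8 lists adverse events, laboratory changes, vital signs and ECOG, but not ECG.
- Section 8.5 covers laboratory tests only. Section 8.6.1 limits vital signs to weight and blood pressure.
- Section 4 says how continuous data are described and that summaries are by arm, but schedules no QTc table.
- Section 4.8 says substantive changes to protocol analyses will be documented in a revised plan. For Section 8.8, the version history (Table 2) records only a clarification about averaging QTcF measurements.

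**What would the counts show?** The plan states no figure for QTc, so there is none to reproduce. What follows is an illustration.

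Inputs from the documents:

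- mean change 10-15 ms at 140 mg (Protocol 6.5.2.10);
- 94 subjects per arm (Protocol 9.6);
- median treatment of about 11 months (Protocol 3.2), which on the Appendix A schedule gives about six post-dose ECGs (W5, W9, W13, W25, W37, W49).

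Assumptions not in the documents:

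- normally distributed changes with SD 15, 20 or 25 ms and the same mean at every visit;
- between-visit correlation 0.5;
- effect proportional to dose, so 60 mg gives 10 × 60/140 = 4.3 ms to 15 × 60/140 = 6.4 ms.

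At a single visit, P(change > 60) = 1 − Φ((60 − μ)/SD). For μ = 15 and SD = 20 this is 1 − Φ(2.25) = 0.0122, and 94 × 0.0122 = 1.15 subjects.

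SAP 8.8 does not restrict the count to one visit; Section 4.5 bounds it by the safety observation period. The relevant probability is therefore that of ever crossing. With six equally correlated visits it is 1 − ∫ Φ((t − √0.5·z)/√0.5)⁶ φ(z) dz, where t = (60 − μ)/SD. Multiplied by 94:

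| SD (ms) | 140 mg, one visit | 60 mg, one visit | 140 mg, ever in six | 60 mg, ever in six |
|---|---|---|---|---|
| 15 | 0.04-0.13 | 0.01-0.02 | 0.2-0.7 | about 0.1 |
| 20 | 0.58-1.15 | 0.25-0.35 | 2.8-5.2 | 1.3-1.7 |
| 25 | 2.1-3.4 | 1.2-1.5 | 9-13 | 5.5-6.6 |

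For QTcF above 500 ms, suppose the XL184-301 statement means 0 of the 214 cabozantinib-treated subjects in Protocol Table 1-4. The upper one-sided 95% limit is then 1 − 0.05^(1/214) = 1.39%, or at most about 94 × 0.0139 = 1.3 subjects per arm.

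**What would a table of means show?** The 95% CI half-width for the between-arm difference in mean change at W5D1 is 1.96 × SD × √(2/94):

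- SD 15: 4.3 ms
- SD 20: 5.7 ms
- SD 25: 7.1 ms

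Under dose proportionality the true difference would be 10 − 4.3 = 5.7 ms to 15 − 6.4 = 8.6 ms. Power at two-sided 0.05 would be 74-97% (SD 15), 50-84% (SD 20) and 35-65% (SD 25). All of this assumes that every subject has a W5D1 ECG.

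**The case against.** The strongest reply is that the SAP does not breach the protocol. Section 9.4.3 asks for changes or shifts. It names no mean, visit, interval or band, and Protocol Section 9 leaves detail to the SAP. A count of subjects with an increase above 60 ms, shown by arm, is derived from change from baseline. This stands: a reader might infer that the SAP drops a required analysis or contradicts the protocol, and the documents do not support that. The SAP meets the wording in a minimal form, thinner than it gives the other two items in the same sentence.

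The cut-offs are not arbitrary either. 500 ms and 60 ms are the protocol's own criteria for acting on a prolonged QTcF (Sections 5.5.4 and 6.5.2.10), so counting those crossings is useful and should stay. ECG abnormalities that change management are also reported as adverse events and so reach the by-arm tables. Neither route gives the size of the average shift.

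It can also be said that QTc is not among the adverse events named in the safety endpoint (Protocol 2.1), and that Protocol 9.4 plans no formal safety comparisons. Both are true. They limit the remedy to descriptive or exploratory output, which SAP Section 8 allows.

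**Conclusion.** The concern holds as a narrowing of the QTc analysis. As written, SAP 8.8 would not estimate the protocol's own 10-15 ms mean QTcF effect in either arm, or describe whether it differs between doses. That rests on the text alone.

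The size rests on assumptions, and two stronger readings go too far:

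- **That both counts would be near zero and so look like no difference.** This holds for the 60 ms count only at the smaller SDs. At SD 25 ms, about 9-13 versus 5.5-6.6 subjects could cross at some visit.
- **That 60 mg prolongs QTcF less.** No QTcF effect at 60 mg is given anywhere. The protocol says a concentration-QTc relation could not be firmly established. The arms also use formulations for which bioequivalence could not be concluded at 140 mg (Protocol 1.4.3.3). The assumed 5.7-8.6 ms difference, and the 35-97% power for it over SD 15-25 ms, are therefore illustrative.

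The CI half-width of 4.3-7.1 ms needs only the SD and the number of subjects. It shows that the ECGs already scheduled could inform the dose question to a useful degree.

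**What to change.** In SAP 8.8, keep both counts and add:

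1. Descriptive statistics for QTcF, actual value and change from baseline, by scheduled visit and arm (W5D1, W9D1, W13D1, then every 12 weeks). Baseline is the last pre-dose value, as in SAP 4.1. State whether the investigator or ERT values are used. Also state that a visit with a single ECG contributes that value, because Protocol 5.5.4 takes single ECGs at scheduled visits while SAP 8.8 speaks of triplicate averages.
2. A shift table of worst post-baseline QTcF against baseline, by arm.
3. Optionally, the between-arm difference in mean change at W5D1 with its 95% CI, labelled exploratory. Protocol 9.4.3 does not ask for this; it is an addition.

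If the sponsor prefers the counts alone, the SAP should record and justify that choice under Section 4.8.

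The cost is a few lines of SAP text and one or two more tables from ECGs already scheduled. There are no new procedures or subjects, and alpha is unaffected. The downside is more exploratory safety output, with later visits describing only subjects still being followed. The change concerns reporting only and leaves every dosing and QTc management rule as it is.
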